8.1 Sample Size

A per-group sample size of 44 evaluable participants provides 85% power to detect a decrease of 90% in the total number of gadolinium-enhancing T1 lesions, summed over scans at Week 12, 16, 20, and 24, between each M2951 group versus placebo at the 2-sided 5% level, using the Wilcoxon rank-sum test, where the p-value is evaluated using a continuity-corrected normal approximation to the test statistic. Power was evaluated via simulation in R of the Wilcoxon test (wilcox.test) applied to lesion count data generated according to a NB distribution, with mean $\lambda_t = 0.55$ and shape parameter $\Upsilon_t = 14.0$ for a given M2951 group (Υ_t based on rituximab data) (2), and mean $\lambda_c = 5.5$ and shape parameter $\Upsilon_c = 7.256$ for the placebo group (λ_c and Υ_c based on placebo data) (2), yielding a lesion rate ratio of $\lambda_t/\lambda_c = 0.10$. Approximately 50 participants will be randomized per group to protect against a loss of information due to a 12% drop-out rate over 1 year, and to provide for an adequate assessment of safety. (Note that the NB distribution parameterization assumed here implies lesion count variance equals $\lambda + \lambda^2 \Upsilon$ for a given treatment group.)

Approximately 250 participants will enter the main study. Assuming an 80% rate of continuation to OLE, approximately 200 participants are expected to enter the OLE Period.

FWER at the primary analysis will be controlled at the 2-sided 0.05 significance level for the 3 comparisons of M2951 dose group versus placebo using the Hochberg procedure.

8.2 Randomization

Eligible participants will be randomized 1:1:1:1:1 to treatment with placebo, low-dose M2951 (25 mg once daily), mid-dose M2951 (75 mg once daily), high-dose M2951 (75 mg twice daily), or Tecfidera (administered twice daily at a final dose of 240 mg), through a central randomization process by an IWRS, stratified according to region (USA or Western Europe, Eastern Europe and CCI , Eastern Europe and not CCI , and RoW).

8.3 Endpoints

8.3.1 Primary Endpoints

The primary endpoint is the total number of gadolinium-enhancing T1 lesions at Week 12, 16, 20, and 24. The primary analysis is a comparison of each M2951 dose arm versus placebo based on this endpoint, with a supportive test for dose-response.

8.3.2 **Secondary Endpoints**

Key secondary endpoints to evaluate the efficacy and safety of M2951 compared to placebo:

- ARR, based on protocol-defined qualified relapses, at Week 24;
- Qualified relapse-free status at Week 24;
- Change from Baseline in EDSS at Week 24;
- Safety as assessed by the nature, severity, and occurrence of AEs; vital signs; ECGs: absolute concentrations and change from Baseline in Ig levels; absolute numbers and change from Baseline in B cells; and clinical laboratory safety parameters (duration of placebo treatment group limited to 24 weeks).

Additional secondary endpoints:

To evaluate the efficacy of M2951 compared to placebo:

- Total number of new Gd+ T1 lesions at Week 12, 16, 20, and 24;
- Mean per-scan number of Gd+ T1 lesions at Week 12, 16, 20, and 24;
- Total number of new or enlarging T2 lesions at Week 12, 16, 20, and 24;
- Change from Baseline in the volume of Gd+ T1 lesions at Week 24;
- Change from Baseline in the volume of T2 lesions at Week 24.

To evaluate efficacy within M2951 dose groups:

- Number of Gd+ T1 lesions at Week 48;
- Number of new Gd+ T1 lesions at Week 48;
- ARR, based on protocol-defined qualified relapses, at Week 48;
- Qualified relapse-free status at Week 48;
- Change from Baseline in EDSS at Week 48;
- Number of new or enlarging T2 lesions at Week 48;
- Change from Baseline in the volume of Gd+ T1 lesions at Week 48;
- Change from Baseline in the volume of T2 lesions at Week 48.

To evaluate the efficacy and safety of Tecfidera:

- Total number of gadolinium-enhancing T1 lesions at Week 12, 16, 20, and 24;
- ARR, based on protocol-defined qualified relapses, at Week 24;
- Qualified relapse-free status at Week 24;
- Change from Baseline in EDSS at Week 24;

- Safety as assessed by the nature, severity, and occurrence of AEs; vital signs; ECGs; absolute concentrations and change from Baseline in Ig levels; absolute numbers and change from Baseline in B cells; and clinical laboratory safety parameters;
- Total number of new Gd+ T1 lesions at Week 12, 16, 20, and 24;
- Mean per-scan number of Gd+ T1 lesions at Week 12, 16, 20, and 24;
- Total number of new or enlarging T2 lesions at Week 12, 16, 20, and 24;
- Change from Baseline in the volume of Gd+ T1 lesions at Week 24;
- Change from Baseline in the volume of T2 lesions at Week 24;
- Number of Gd+ T1 lesions at Week 48;
- Number of new Gd+ T1 lesions at Week 48;
- ARR, based on protocol-defined qualified relapses, by Week 48;
- Qualified relapse-free status at Week 48;
- Change from Baseline in EDSS at Week 48;
- Number of new or enlarging T2 lesions at Week 48;
- Change from Baseline in the volume of Gd+ T1 lesions at Week 48;
- Change from Baseline in the volume of T2 lesions at Week 48.

8.3.4 Endpoints for Open-label Extension Period

The endpoints for the OLE Period are as follows:

- Efficacy and CCI endpoints at Week 48, 96, 144, 192, 240, 288, 336, and 384.
 - o Number of gadolinium-enhancing T1 lesions;
 - o ARR, based on protocol-defined qualified relapses;
 - Qualified relapse-free status;
 - o Change from baseline in disability score based on EDSS score;

• Safety as assessed by the nature, severity, and occurrence of AEs; vital signs; ECGs; absolute concentrations and change from Baseline in Ig levels; CCI; and clinical laboratory safety parameters.

8.4 Analysis Sets

For the purposes of analysis, the following analysis sets are defined:

Safety Analysis Set

The Safety Analysis Set consists of all participants who receive at least 1 dose of trial treatment. Participants will be analyzed according to the actual treatment they receive.

Intent-To-Treat Analysis Set

[figure not shown]
The Intent-To-Treat ITT Analysis Set consists of all participants randomly allocated to a treatment, based on the intention to treat "as randomized" principle (i.e., the planned treatment regimen rather than the actual treatment given in case of any difference).

Modified Intent-To-Treat Analysis Set

The mITT Analysis Set consists of all participants who belong to both the ITT and Safety Analysis Sets, and who have at least one baseline and one postbaseline MRI assessment.

Per-Protocol (PP) Analysis Set

The PP Analysis Set consists of all participants who belong to the mITT Analysis Set, complete 24 weeks of treatment, and do not have any important protocol deviations.

Open-Label Extension Analysis Set

The OLE Analysis Set consists of all participants who receive at least 1 dose of M2951 during the OLE.

8.5 Description of Statistical Analyses

8.5.1 General Considerations

A general description of the statistical methods to be used to analyze the efficacy and safety data is outlined below. Prior to partial locking the database for the primary analysis, a detailed IAP will be developed.

Continuous variables will be summarized descriptively using the number of observations, mean, SD, median, first quartile (Q1), third quartile (Q3), minimum, and maximum. Categorical variables will be summarized using frequency counts and percentages. The denominator for the percentages will be the total number of participants in the treatment group and analysis set being presented, unless otherwise specified (e.g., on some occasions, percentages may be calculated out of the total number of participants with available data at a particular time point).

All tests of treatment effects will be conducted at a 2-sided α -level of 0.05. P-values and the 95% CIs will be presented where applicable. Actual p-values will be interpreted based on the multiple testing strategy. Treatment comparisons for each data type are described in later sections. Alternative or additional statistical methods may be used as appropriate as outlined in the IAP.

Data from all investigative sites will be pooled for all planned analyses. Analysis of individual site findings or country findings will be considered if necessary. For those measures that are analyzed using change from baseline scores, observed scores may also be presented descriptively.

The procedures to be followed in relation to handling missing, unused, or spurious data will be described in the IAP. The IAP will provide the definition(s) of Baseline measurement as required.

All participants will be included in individual participant data listings.

Any changes to the data analysis methods described in the protocol will require an amendment only if a principal feature of the protocol is affected. Any other changes to the planned data analysis that does not require a protocol amendment will be described in the IAP and the CSR.

8.5.2 Analysis of Primary Endpoint

Primary Efficacy Endpoint

The primary analysis of total number of Gd+ T1 lesions, at Week 12, 16, 20, and 24, will be an estimate of lesion rate ratio, together with associated 95% CI and p-value, comparing each M2951 dose group to placebo, based on a NB model, where the offset will be based on the log of number of scans, with M2951 dose or placebo group as a factor and adjustment for covariates based on randomization strata and baseline MRI activity. Other covariates may be considered. Should the model fail to converge, the primary analysis will be an estimate of the shift in location of the distribution of the Gd+T1 lesion count via the Hodges-Lehman estimate, together with associated 95% CI and p-value based on the stratified Wilcoxon rank-sum test, comparing each M2951 dose group to placebo. Descriptive statistics for the total number of Gd+ T1 lesions, at Week 12, 16, 20, and 24, will be provided for each treatment group.

The primary analysis of the primary endpoint will be based on the mITT analysis set, with supportive analyses based on the ITT and PP analysis sets. If the primary analysis is comprised of NB modeling, the computed p-value testing the null hypothesis H_0 : RR = 1.0 for each M2951 dose group will be reported, where RR denotes lesion rate ratio comparing a given M2951 dose group to placebo. If the primary analysis must be nonparametric due to model nonconvergence, the computed p-value testing the null hypothesis H_0 : $P(X < Y) + 0.5 \times P(X = Y) = 0.5$, via the stratified Wilcoxon rank-sum test, for each M2951 treatment group will be reported, where X denotes the primary endpoint evaluated for a participant in a given M2951 treatment group, and Y denotes the primary endpoint evaluated for a participant in the placebo group. The FWER, i.e., overall type I error rate for the primary analysis, will be controlled at the 0.05 level by testing the 3 M2951 hypotheses for the low, mid, and high dose groups using the Hochberg procedure. A test for a monotonic dose-response relationship, between ordered M2951 dose (low, mid, high) and the primary efficacy endpoint, will be performed as a supportive analysis.

No formal comparisons between the Tecfidera arm and any other treatment group will be performed for the primary endpoint.

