The Family-wise Type I error rate (FWER) at the primary analysis, due to multiple comparisons of M2951 dose to placebo based on the primary endpoint, will be controlled at the 2-sided 0.05 significance level using the Hochberg procedure.

Primary Endpoint

The primary analysis of total number of Gd+ T1 lesions, Week 12, 16, 20, and 24, will be an estimate of lesion rate ratio, together with associated 95% confidence interval (CI) and p-value, comparing each M2951 dose group to placebo, based on a negative binomial (NB) model, where the offset will be based on the log of number of scans, with M2951 dose or placebo group as a factor, and adjustment for covariates based on randomization strata and baseline MRI activity. Other covariates may be considered. Should the model fail to converge, the primary analysis will be an estimate of the shift in location of the distribution of total number of Gd+ T1 lesions via the Hodges-Lehman estimate, together with associated 95% CI and p-value based on the stratified Wilcoxon rank-sum test, comparing each M2951 dose group to placebo. Descriptive statistics for the total number of Gd+ T1 lesions, Week 12, 16, 20, and 24, will be provided for each treatment group. The primary analysis will be based on only the M2951 dose groups and placebo group.

Other Efficacy Endpoints, Baseline to 24 weeks:

The comparison of a M2951 treatment group to placebo group using ARR at Week 24 will be based on the rate ratio estimated from an NB model for qualified relapse count, with offset equal to the log of years on study, with M2951 dose group or placebo group as a factor, and adjustment for covariates based on randomization strata and prebaseline relapse activity. The comparison of a M2951 treatment group to placebo group using proportion qualified relapse-free at Week 24 will be based on the odds ratio estimated from a logistic model for the odds of a participant being qualified relapse-free, where participants who discontinue prior to Week 24 without having a qualified relapse are counted as not being qualified relapse-free at Week 24, with M2951 dose group or placebo group as a factor, and adjustment for covariates based on randomization strata and prebaseline relapse activity. The comparison of a M2951 treatment group to placebo group using change from Baseline in EDSS at Week 24 will be based on a stratified Wilcoxon rank-sum test, with strata defined by baseline EDSS and randomization strata.

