3.2 Benefit-Risk

Benefit

M2951 is the first agent with a mechanism of action that directly targets both B cells and myeloid cells. In the primary analysis of this study (MS200527_0086), evobrutinib significantly decreased the number of T1 Gd+ lesions at Weeks 12, 16, 20, and 24 in participants with RMS. Similar to the relationship seen for the MRI endpoints, evobrutinib was associated with a lower ARR compared to placebo. During the OLE period, the efficacy was maintained and similar to that observed in the primary analysis (26). Post-hoc analyses show that evobrutinib significantly reduced blood levels of neurofilament light chain and slowly expanding lesion volume, markers of ongoing CNS-compartmentalized inflammation and neurodegeneration that predict long-term disability (27, 28). This coupled with the detection of evobrutinib in the cerebrospinal fluid of participants with RMS (29) support the potential for evobrutinib to have biologically relevant effects directly within the CNS by acting on mechanisms of progression. Though data suggests evobrutinib inhibits immune inflammation association with progression, participants treated with evobrutinib successfully develop humoral responses to COVID-19 vaccines (30). It is reasonable to anticipate that M2951 may represent a significant advance in the treatment of MS.

Important Identified Risk

- Important Identified Risk: Drug-Induced Liver Injury
 - As of July 2022, more than 2,490 participants have been exposed to evobrutinib in completed and ongoing clinical studies including healthy volunteers, participants with RMS, SLE, or RA, and participants with renal and hepatic impairment. The incidence of SAEs and treatment-emergent adverse events (TEAEs) leading to

- withdrawal of study intervention was $\leq 10\%$ in completed SLE, RA, or RMS studies.
- Overall, evobrutinib demonstrated manageable tolerability based on the completed and ongoing clinical studies across various indications. Observed TEAEs resolved after treatment discontinuation and did not result in permanent disabilities. In the ongoing blinded Phase III studies, cases of drug-induced liver injury (DILI) have been reported, which were typically asymptomatic and were resolving after drug discontinuation. The TEAEs have been primarily mild to moderate in severity.

Important Potential Risks

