The purpose of this Integrated Analysis Plan (IAP) is to document technical and detailed specifications for the Final Analysis (FA) of data collected for protocol MS200527-0086 considering the early termination of the study; the primary endpoints of the phase 3 MS200527_0080 and MS200527_0082 studies were not met). The IAP is based upon Section 8 (Statistics) of the trial protocol dated 06 July 2023 (Version 8.0) and is prepared in compliance with International Conference on Harmonization E9.

This FA data report will include summaries of participant disposition, demographics, baseline characteristics, medical history, previous and concomitant medications, treatment exposure, efficacy evaluations, adverse events (AEs), deaths, selected laboratory parameters, vital signs, ECGs, and other endpoints related to safety monitoring up to the end of the study.

6 Objectives/Endpoints of the Final Analysis

The objective of the OLE Period of this study is to evaluate the long-term safety, efficacy, and HRQoL of M2951 for an additional 8 years, at an initial dose of 75 mg once daily which was eventually switched to 75 mg twice daily.

Endpoints for OLE Period:

- Efficacy and CCI endpoints at Week 48, 96, 144, 192, 240, 288, 336 and 384.
 - Number of gadolinium-enhancing T1 lesions;
 - ARR, based on protocol-defined qualified relapses;
 - Qualified relapse-free status;
 - Change from baseline in disability score based on EDSS score;

Safety as assessed by the nature, severity, and occurrence of AEs; vital signs; ECGs; absolute concentrations and change from Baseline in Ig levels;
 ; and clinical laboratory safety parameters.

For the Final Analysis, selected safety and efficacy endpoints based on data from OLE Day 1 to the end of the study will be evaluated.

For more details on the main study objectives please review section 4 Trial Objectives of the protocol.

7 Sample Size/Randomization

Sample size and randomization is described in the IAP for the primary analysis/blinded extension analysis performed after completion of the Double-Blind Period (DBP) of the study (Week 48/Week 52).

8 Overview of Planned Analyses

The protocol describes a total of 5 analyses that should be performed for this study. 4 of them have already been conducted according to the protocol. These are:

- Primary Analysis (when 100% of participants enrolled reached Week 24 of treatment, or prematurely discontinued from treatment)

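### If the negative binomial model fails to converge, the fallback Hodges-Lehmann shift is an uninformative primary estimate: under the planning distributions it is usually exactly 0 even when its paired Wilcoxon test is significant

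*Protocol*

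**What the plan says.** The primary analysis of total Gd+ T1 lesions over Weeks 12, 16, 20 and 24 is an NB rate ratio for each M2951 dose against placebo. A nonparametric analysis replaces it only on non-convergence. Protocol 8.5.2 then states that "the primary analysis will be an estimate of the shift in location of the distribution of the Gd+T1 lesion count via the Hodges-Lehman estimate". The interval and p-value reported with that shift are to be taken from a Wilcoxon test stratified by the randomization factors. The Protocol Synopsis (Statistical methods, Primary Endpoint) gives the same fallback: "an estimate of the shift in location of the distribution of total number of Gd+ T1 lesions via the Hodges-Lehman estimate".

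Protocol 8.5.2 also names what the test targets: "If the primary analysis must be nonparametric due to model nonconvergence, the computed p-value testing the null hypothesis" is followed by P(X<Y)+0.5P(X=Y)=0.5, with X the M2951 count and Y the placebo count. No estimate of that probability is planned. The text does not say how the Hodges-Lehmann (HL) shift is to be stratified or how its CI treats ties.

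The planning distributions are in Protocol 8.1: "Power was evaluated via simulation in R of the Wilcoxon test (wilcox.test) applied to lesion count data generated according to a NB distribution". Protocol 8.5.1 defers detail to another document: "Prior to partial locking the database for the primary analysis, a detailed IAP will be developed". That primary-analysis plan is not among the documents supplied; the SAP provided covers the Final Analysis of the open-label extension.

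**The concern.** The HL shift estimates the median of all M2951-minus-placebo pairwise differences. The Wilcoxon test addresses the probability that a placebo count exceeds an M2951 count, with ties counted half. The two move together when one distribution is close to a shifted copy of the other. Counts that are mostly zero in both groups are not of that kind, because lesion reduction then shows up mainly as more zeros and a shorter upper tail.

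In the fallback, the HL shift would be the headline effect estimate. At stake is whether a reader of a significant result would also get an effect size and CI that say anything about its magnitude.

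**Working it through.** **Inputs (Protocol 8.1).** 44 evaluable per group; two-sided 5%; continuity-corrected Wilcoxon. M2951: NB with mean 0.55 and shape 14.0. Placebo: NB with mean 5.5 and shape 7.256. Variance = λ + λ²Υ. Protocol 8.2 gives four region strata without sizes. Assumed here: several splits from equal to very uneven (such as 2/20/20/2 per arm), with no stratum effect.

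**The plan's own figure.** Simulating the Wilcoxon test gives 84.5-84.9% power against the stated 85%, so the parameters are read correctly.

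**Zero fractions.** P(0) = (1+λΥ)^(-1/Υ).
- Placebo: (1 + 5.5×7.256)^(-1/7.256) = 40.908^(-0.1378) = 0.600.
- M2951: (1 + 0.55×14)^(-1/14) = 8.7^(-0.0714) = 0.857.

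**The tested quantity.** Summing the NB probabilities gives P(X<Y) = 0.379, P(X=Y) = 0.520 and P(X>Y) = 0.100. So P(X<Y)+0.5P(X=Y) = 0.379 + 0.260 = 0.640 after rounding (null 0.5).

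**The estimated quantity.** X<Y requires Y>0, so P(X<Y) ≤ 1 − 0.600 = 0.40. P(X>Y) is also below one half, so the median of X−Y is 0. The 0.40 bound does not depend on the size of the reduction. It does depend on more than half of placebo participants being lesion-free.

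**Simulation, 44 per group, 90% reduction.**

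| Quantity | Share of trials |
|---|---|
| HL exactly 0, unstratified | 95.0-95.5% |
| HL exactly 0, pooled within strata | 94.0-94.8% |
| Stratified (van Elteren) test rejects | 83.0-84.6% |
| HL exactly 0 and stratified test rejects | about 79-80% |
| HL exactly 0, averaged over strata | about 7-41% (including runs at 50 per group) |

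The averaged form remains small; with size weights its median is about -0.25 lesions. An unweighted sum of stratum statistics, in place of van Elteren weights, rejects in 80-84%. At 50 per group, the unstratified HL is 0 in about 96% of trials and the stratified test rejects in about 88%. With total suppression on M2951, the HL is still 0 in 88.6% of trials while the unstratified test rejects in 100%.

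**The CI.** The documents give no formula, so the unstratified order-statistic interval was used. It includes 0 in more than 99.9% of all trials. In rejecting trials 0 was never strictly inside it. Apart from under 0.1% of trials in which it lay wholly below 0, the interval was [negative, 0] (about 49% of all trials with untied variance, 36% with tie correction) or [0, 0] (about 36% and 49% respectively).

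**Sensitivity to the placebo zero fraction (assumed values, mean kept at 5.5).** HL is exactly 0 in 70% of trials at 51% zeros, 44-46% at 46%, and 14-15% at 39%.

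**The case against.** The strongest reply is about reach. This is a fallback, and nothing in the documents suggests that it was triggered. SAP Section 8 says of the five planned analyses that "4 of them have already been conducted according to the protocol", the primary analysis among them. Protocol 3.2 reports that "evobrutinib significantly decreased the number of T1 Gd+ lesions at Weeks 12, 16, 20, and 24 in participants with RMS" without naming the analysis used. The unseen primary-analysis plan may have fixed the stratified form of the HL shift and its CI. All of this stands, and it limits the point to a question plus a conditional addition.

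A second reply is that the share of exact zeros depends on how the shift is stratified. That also stands: averaging over strata makes exact zeros much less common.

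A third is that HL with Wilcoxon is a conventional pairing, and that group descriptive statistics and a dose-response test are planned anyway. They are, and they soften the loss. They do not supply a between-group estimate and CI for the quantity tested.

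Four stronger readings are tempting but unsupported:
- *The CI contradicts the p-value.* A reader might take a CI that includes 0 as inconclusive. In rejecting trials it only reaches 0 at its edge, because counts are integers, and never extends to harm.
- *The same contrast is shown at smaller reductions.* Keeping shape 14 on M2951, the unstratified test rejects in 41% and 56-58% of trials at 50% and 70% reductions. But it already rejects in 22-23% with equal means and that shape. With shape 7.256 in both groups the figures are about 11% and 25%. That series mixes dispersion with lesion reduction.
- *The HL shift misses the mean difference.* It does not target a mean, so the difference in means is not a fair yardstick.
- *The reported primary result is in doubt.* The p-value and Hochberg control do not depend on the HL shift.

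**Conclusion.** The point holds in a limited form. Conditional on NB non-convergence, the fallback as written pairs a test with an estimate that does not measure what is tested. Under the plan's own distributions the population shift is 0 whatever the reduction, and an unstratified or pooled shift comes out as exactly 0 beside a significant test in about 79-80% of trials. The estimate and CI would be uninformative; they would not contradict the test.

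This rests on the Protocol 8.1 parameters, in particular a placebo zero fraction above one half, and on assumed strata with no stratum effect. Exact zeros become less common as the placebo zero fraction falls or if stratum estimates are averaged. The non-convergence rate is unknown and none is claimed. A low-priority item to consider.

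**What to change.** First confirm whether the NB model converged at the primary analysis. If it did, a one-line statement closes the point.

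Only if the fallback was used, report the stratified Mann-Whitney probability P(X<Y)+0.5P(X=Y), the quantity in the stated null, with its 95% CI as the effect estimate. Keep the HL shift as supportive and state how it was stratified. In simulation under the planning values, the interval for this probability covers in 94.6-94.8% of trials and excludes 0.5 in 85% (median interval 0.55-0.73). With no effect it excludes 0.5 in 5.1%.

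The cost is one extra estimate and CI in the report. The replacement has its own limits:
- It is a probability, not a number of lesions.
- Under these assumptions it cannot exceed about 0.40 + 0.5×0.60 = 0.70, even with total suppression.
- It responds to dispersion as well as to the mean: it is 0.563 with equal means and shapes 14 and 7.256.

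It should therefore be read beside the planned group means.
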